NCT02862210

Low-dose lithium for the treatment of behavioral symptoms in Frontotemporal Dementia Standard Operating Procedures Manual Version date 31May2021

Introduction

The Alzheimer's Drug Discovery Foundation funded a study titled "Low-dose lithium for the treatment of behavioral symptoms in Frontotemporal Dementia," which examines the efficacy and side effects of low dose lithium treatment for agitation/aggression/repetitive behaviors in 60 patients with FTD in a randomized, double blind, placebo-controlled 12-week trial.

Lithium carbonate or placebo will be started at an oral dose of 150 mg daily, with subsequent dose titration to 300mg/day at the 2-week visit, 450mg/day at the 4-week visit, and 600mg/day (maximum daily dose) at the 6-week visit. This upward dose titration will occur if clinically indicated, tolerated by the patient, and based on real/sham lithium blood level. An absence of response at lower doses without intolerable side effects is defined as clinically indicated. Assessments will take place at study entry (0 weeks), 2, 4, 6, 8, and 12 weeks, and the time-point of protocol exit for dropouts. Lithium levels will be drawn approximately 12-14 hours after the last dose.

Our primary outcome measures will be the Neuropsychiatric Inventory and the Clinical Global Impression scales.

Optimal target serum levels of lithium will be between 0.2 to 0.6 mmol/L due the risk of dropout due to lithium toxicity at higher levels. Clinical response of symptoms and side effects experienced by the patient will be primary in guiding oral lithium dose adjustment, and will override the information obtained from serum lithium levels if such a choice needs to be made.

This study will provide useful data on the efficacy and side effects of low-dose lithium treatment for FTD patients with symptoms of agitation/aggression, and possibly for other behavioral symptoms such as aberrant motor behaviors. The potential utility of lithium would provide an alternative for patients who show no/minimal response to or experience intolerable side effects while on antidepressants and antipsychotics.

During COVID, it was decided that the protocol would be updated to allow for a portion of the study visits to occur remotely. This was largely to reduce risks to participants once the study reopened (I.e. to minimize time traveling to a hospital), but also, we hoped this would make the study less burdensome to patients and study partners moving forward.

Management of Trial (ADDF, IRB, DSMB)

Coordinator Role

The research team at CUMC is responsible for the proper conduct of project and data management. The research coordinator will be responsible for communications essential to the trial, such as those with the grant awarder (the Alzheimer's Drug Discovery Foundation, ADDF), the Data and Safety Monitoring Board (DSMB), the Institutional Review Board (IRB), and the research pharmacy.

Alzheimer's Drug Discovery Foundation (ADDF). This trial is funded through a grant awarded by the ADDF. An interim progress report to the ADDF will be generated by the lead site staff every 6 months, with reports due each year on April 30st and October 30th. A final progress report will be submitted upon completion of the grant award. Resources to prepare the report are here: https://www.alzdiscovery.org/research-and-grants/resources.

The following information will be included in reports to the ADDF:

- IRB approved changes to the protocol
- Subject recruitment, screening, and enrollment numbers
- Reports of all serious adverse events
- Summary of guidance from the DSMB

The research coordinator is responsible for writing the scientific portion of the report (and reviewing with [name]). The financial coordinator (currently [name]) will prepare the financial portion and will send both parts to the grant office. Reports should be prepared ~1 month before they are due and sent to [name] no later than 2 weeks before they are due for final approval.

After the progress report has been submitted, the ADDF will reach out to schedule a teleconference with [name] and the research coordinator to discuss the materials of the report.

Recruitment

Sources

- 1. Direct referral (from DPO clinician or outside clinician)
- 2. Identified via DPO tracker (log of patients seen by DPO doctors)
- 3. Identified via [name]'s clinic schedule
- 4. Self-referred (via advertisement)

Procedure (broadly)

- 1. Confirm diagnosis
- 2. Confirm eligibility (see details below under "Prescreen")
- 3. Confirm interest

If DPO patient:

- 1. Review chart for eligibility
 - a. Neurologist clinical notes, MRI/PET scan record, neuropsychological testing
 - b. Generally we trust an internal diagnosis, but it is good to confirm and particularly to look for indications of agitation or repetitive behaviors
- Contact treating physician to ask for referral (or discuss with [name] if his patient)

 In email, include patient name / MRN, brief description of study, summary of information relevant to patient eligibility.

3. If referred, reach out to the patient's contact to describe study, determine interest, and confirm eligibility

If outside referral:

- 1. Discuss by phone to assess potential eligibility
 - a. Possible diagnosis of FTD, appropriate symptoms, access to study site
- If potentially eligible, request record of outside neurological records for review

 Neurologist clinical notes, MRI/PET scan record, neuropsychological testing

3. Upon review of records, if insufficient information to determine eligibility, refer them to make a clinical appointment with [name], after which you can reassess eligibility

For both:

4. If eligible, send study flyer & consent form for review. Plan second call to review information, answer questions, and schedule baseline visit. This can be multiple communications if necessary, but spreading the communication over too long a period runs the risk that they will forget key details. It is good practice to regularly review key components of the study and participation.

- 1. Points of emphasis:
 - 1. The study is voluntary and participation can be ended at any time
 - 2. It is a placebo-controlled study, so there is a 50% chance of receiving placebo, but at the end of the trial participants on placebo may be started on lithium off-label if clinically indicated

3. Study duration (12 weeks), visit commitment (1-3 hours every 2 weeks, first and last in-person, the rest over zoom)

5. It may also be appropriate to describe observational study options (ALLFTD / NAPS) to the potential participant. This can be coordinated in advance with [name] / NAPS team and will impact scheduling details. In this case, send flyers for these studies as well & refer for conversation with primary study coordinator.

6. All chart reviews and patient communications should be documented in the **Research Screening Log** excel file or in Ripple

a. Chart reviews are regularly entered into the DPO review tab for outside DPO doctors and into the DPO Visits [name] Eligibility excel (managed by [name]) for [name]'s patients.

b. Any patients potentially eligible for lithium should be transferred to the Lithium Screen tab, where notes on eligibility review can be added. It should be specified on this tab whether the patient was subsequently contacted (and transferred to the phone screen tab) or was determined ineligible

c. Once telephone contact for recruitment has been approved, patients should be entered into the phone screen tab, where contact information and recruitment notes will be regularly updated.

Prescreening

To comply with Health Insurance Portability and Accountability Act (HIPAA) regulations, we applied for a partial waiver of HIPAA and were granted a partial waiver for telephone screens and a full waiver for the purpose of accessing an existing database or records to identify potential research subjects (Forms: "Request for HIPAA Waiver Authorization and/or Waiver of Consent)". These waivers were granted with initial IRB approval of the protocol.

- 1. For the prescreening process, review patient charts for:
 - a. Age
 - i. (40-85)
 - b. Active medical conditions
 - i. (include: bvFTD, svPPA, nfvPPA with behavioral symptoms of agitation, aggression, disinhibition, repetitive behaviors, aberrant motor movements, etc)
 - ii. (exclude: Parkinson's disease, Lewy body disease, multiple sclerosis, CNS infection, HD, amyotrophic lateral sclerosis, other major neurological disorder, clinical stroke with residual neurological deficits e.g. small infarcts, lacunes, periventricular disease (if these cerebrovascular diseases are found from MRI in absence of stroke it will not lead to exclusion), medical contraindication to lithium treatment or prior history of

intolerability to lithium treatment such as resting tremor causing functional impairment, untreated thyroid disease or any abnormal thyroid function, unstable cardiac disease, schizophrenia, other psychosis or bipolar 1 disorder, current or last 6 month alcohol or substance abuse, major depression or suicidality, acute, severe, unstable medical illness (e.g. active or metastases cancer will be excluded, but past history of successfully treated cancer will not lead to exclusion).

- c. Current medications
 - i. (exclude: therapeutic or higher doses of diuretics, i.e. hydrochlorothiazide greater than 25mg daily, furosemide greater than 10mg daily, no higher than 1 mg/day of lorazepam for anxiety/insomnia)
- d. Recent Lab results
 - i. (exclude: abnormal TSH, T3, or T4, creatinine level greater than 1.5mg/100ml or a glomerular filtration rate less than 44ml/min/ $1.73m^2$, blood pressure > 170/100 mmHg, heart rate < 50 bpm)
- e. Recent physician evaluation/follow-up notes
 - i. (include: if physician mentions agitation, aggression, or having behavioral disturbances, MMSE 5-30 out of 30, Neuropsych Inventory (NPI) agitation/aggression subscale score or disinhibition subscale score or aberrant motor subscale score ≥ 4 indicating moderate to severe symptoms, or total NPI score ≥ 4)

Screening/Baseline Visit

Since making the protocol hybrid-remote, we have combined the screening and baseline visits into a single in-person visit to increase efficiency and minimize the number of visits to the clinic. This visit will be completed in-person. For a brief checklist to refer to when running the visit, see "Visit Checklists" at the end of this manual.

Study ID

All participants coming in for a screening/baseline visit will be assigned a Study ID, which will be a number from 1001-1999. Even if the participant does not remain in the study, they will retain this study ID and it will not be reassigned.

Consent Procedures

A study physician listed on the site's IRB protocol will obtain voluntary informed consent from patients who retain the capacity consent. Typically, patients with Folstein MMSE greater than 20 out of 30 retain this capacity.

The consent form describes the nature of the procedures and time requirements, potential risks, confidentiality of information, and the rights of research subjects, including their right to withdraw from the research at any time without loss of benefits to which they are otherwise entitled. It is made explicit that this protocol involves a randomized controlled trial in which the patient will be randomly assigned to lithium or placebo for a 12-week period.

Patients' capacity to consent or to assign a surrogate of consent is assessed, as described below. Screening/baseline procedures should be completed on the same day, following consent procedures whenever possible. If not, the screening date should correspond as closely with the informed consent date as possible.

After the informed consent forms are signed, the patient and informant will participate in a screening session. The screening includes structured interviews inquiring about the patient's medical and psychiatric history. To minimize anxiety, patients and informants will be informed about the nature of the interviews beforehand. Patients and informants will also be informed that all findings will be kept strictly confidential.

Consent capacity assessment procedures:

An independent evaluator, an MD or clinical psychologist PhD independent of the research study, will be present to conduct an evaluation to determine whether a patient retains the capacity to consent, and if not, whether they retain the capacity to appoint a surrogate. This will be documented in the research chart. This physician should be familiar with the study and study

personnel, but cannot also be a study physician (typically, this is done by clinical fellows in the Neurology department). Generally, the independent physician makes a decision after observing the study coordinator or study physician explain the study basics to the patient and study partner, and may choose to ask the patient some basic questions to determine understanding (i.e.: "can you describe the study to me in your own words? What are the risks of the study? If you no longer wished to participate, what would you do?").

For patients who lack the capacity to consent, as is expected for most patients in this study, the required NYSPI/Columbia IRB-approved surrogate consent procedures will be followed as detailed below. Patients who lack the capacity to consent will be required to have the capacity to appoint a surrogate, after which the patient will need to appoint the surrogate. The independent evaluator will ask further questions to make this determination (i.e.: "is there someone who you would trust to make a decision for you?"). Out of the patients who lack the capacity to consent, those who also lack the capacity to appoint a surrogate or do not wish to appoint a surrogate will not be included in the study. Under no circumstance will a patient objecting to participation be included in the study. NYSPI PCS forms I-IV should be completed, along with a consent procedure note.

If the patient is determined to have the capacity to appoint a surrogate, two witnesses independent of the research study will be present to bear witness to and declare that the patient is acting willingly and free from duress (one of whom may be the independent physician and the other of whom is usually another RA from the lab). If the patient appoints a surrogate to consent, the CUMC coordinator needs to send notice of this decision, using the NYSPI PCS Policy Letter format, to the Mental Health Legal Service located at [name]. Copies of this notice should be sent to the CUMC IRB, put in the patient chart, and put in the regulatory binder.

Screening/Baseline Evaluation

The visit encompasses completion of the screening-baseline packet to determine eligibility following consent procedures. Once the informed consent process has been completed, all remaining procedures can occur. It is not permitted to collect biological samples (blood) from a patient before informed consent has been obtained.

To decide the order in which measures and procedures will be completed, consider which items are completed by coordinators and which are completed by physicians. An efficient approach to the screening visit could involve a study physician completing the NPI and other interview measures with the patient's informant in one exam room, while the study coordinator completes the MMSE, vitals, blood draws, and EKG with the patient in a separate exam room. Note that the study physician will need to complete a physical exam with the patient as part of the screening visit. Alternatively, the coordinator may do all procedures sequentially, scheduling in a brief period for the study physician to complete the clinical examination. Visit structures may vary participant to participant. Some participants cannot be left alone, and so coordinators may consider allowing them to stay present during the caretaker interviews, if this is not disruptive to the reporting. Similarly, caretakers may vary in the amount of information they provide during interviews, and this can be taken into account for time estimates. It is good to remain flexible during each visit.

At the conclusion of the screening/baseline visit, study staff should know which inclusion/exclusion criteria are met and which are not, with the exception of those that require lab results to determine. If at this point the patient has not been excluded, the participant should be informed that after all lab results are returned, the research pharmacy will ship the study drug kit directly to the participant's home.

The following assessments will be completed at the screening/baseline visit:

Physician-completed:

- Clinical Evaluation & Physical Examination
- CGI (Global Impression of Severity)
- SCID and CSSR-S
- Lawson IDLs
- Simpson-Angus Scale
- Treatment Emergent Symptoms Scale (baseline measure for comparison)

Coordinator-completed

- Confirmation of diagnoses*
- Medical History & Concomitant Medications*
- MMSE (Folstein Mini Mental Exam)
- MDRS (Mattis Dementia rating Scale)
- FBI (Frontal Behavioral Inventory)**
- Zarit Caregiver Burden Interview**
- NPI (Neuropsychiatric Inventory and Stereotypic and Ritualistic Behaviors)**
- Vital signs
- Blood specimens collected (CBC, BMP, Thyroid panel, BDNF) 3 tubes total
- EKG

*Note that much of this can be filled out from past medical records

** For COVID safety or convenience, these may be completed by phone/Zoom after the visit, but completing everything during the in-person evaluation is preferred.

The breakdown between study physician and coordinator is what was agreed upon by [name] and [name], but can be renegotiated as needed depending on who is acting as physician/coordinator.

Sample schedule:

Color-codes
Coordinator
Physician
Coordinator, Physician,
Independent Evaluator

Time	Assessment
30 mins	Consent & Capacity Assessment
30 mins	Physical Exam, SCID, CSSR, CDR,
	Lawson, SAS, TESS, CGI
30 mins	MMSE, MDRS with patient
30 mins	EKG, Blood Draw with patient
45-60 mins	NPI, FBI, Zarit with Study Partner

Note that after the blood draw, samples must be dropped off at the respective labs by 3pm.

- The biomarker core lab is located on PH10-104 through the double doors in the opposite direction of the clinical rooms from the Irving reception area. There is a drop-off bin at the entrance of the lab.
- The CALM lab is located on the 15th floor of the Presbyterian Hospital in room 15-401, where there is a drop-off bin when you enter the lab.

If a patient is ineligible at a screening visit but is still interested in participating in the study, it is up to the clinical judgment of a study physician to decide whether or not to re-screen this patient. Some lab results or vital signs may change over time, making a patient eligible for the study. If a patient is re-screened and found eligible, they are no longer considered a screen fail and their status can be updated on the screening log.

Doubtful Subjects for Inclusion/Exclusion

Obtain recent labs and relevant medical records for potential research recruits whenever possible. Ideally, you will have obtained a recruit's medical records and reviewed them with a study physician prior to a screening visit. If there is any doubt that a recruit will be eligible on one or more specific criteria, study staff should do their best to obtain records and get in contact

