Outcome measures and covariates. Primary outcome: agitation/aggression score (domain score on the Neuropsychiatric Inventory (NPI), continuous measure from 0-12, longitudinal); Secondary outcome: response (dichotomous, based on 30% decrease in NPI core score (sum of domains for motor activity and agitation/aggression) plus a CGI-C score of much improved or very much improved, longitudinal); Exploratory outcome motor activity score on the NPI. Covariates/Predictor variables: 1) demographic characteristics (e.g., gender, race, age); 2) baseline measures of the corresponding outcomes. Other Measures:1) tolerability, as measured by emergent side effects (TESS scores and adverse events) over the course of the 12 week trial; 2) brain derived neurotrophic factor (BDNF) serum levels.

Sample size and randomization: The randomization will be carried out by the statistician and implemented by the pharmacist, who are both otherwise independent of the research team. The randomization sequences will be balanced in blocks of random size to prevent clinicians from guessing what the next patient's treatment might be.

Modeling longitudinal data and testing hypotheses. Modeling longitudinal data and testing hypotheses. All tests will be two-sided; α =0.05; intent-to-treat with data included for all patients with ≥1 post-baseline assessment. We will use generalized linear mixed models (GLMMs; SAS PROC GLIMMIX) for longitudinal data to evaluate study aims. Models will include fixed effects for treatment group, time, group x time interaction, and any baseline covariates found to be unbalanced despite randomization. Prior to analysis, we will examine all variables at all time points for outliers and inconsistencies and examine their distributions.⁴¹⁻⁴³

Primary hypothesis: *Lithium will significantly reduce agitation/aggression as compared to placebo.*

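### The total-score alternative cancels the NPI domain thresholds, and no printed entry rule requires the agitation that is the sole primary outcome

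*Combined protocol and SAP*

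**What the plan says.** Item e of the Prescreening list gives three alternative domain thresholds, "agitation/aggression subscale score or disinhibition subscale score or aberrant motor subscale score ≥ 4 indicating moderate to severe symptoms", and then adds the total score as a fourth alternative: "aberrant motor subscale score ≥ 4 indicating moderate to severe symptoms, or total NPI score ≥ 4". The same list has conditions in words. The diagnosis item asks for "bvFTD, svPPA, nfvPPA with behavioral symptoms of agitation, aggression, disinhibition, repetitive behaviors, aberrant motor movements, etc", and the physician-notes item is met "if physician mentions agitation, aggression, or having behavioral disturbances".

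The list is introduced as a chart review ("For the prescreening process, review patient charts for"). The Recruitment section nevertheless sends staff to it to confirm eligibility, and no other NPI entry rule is printed. The Randomization section requires all inclusion criteria to be met.

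Under Outcome measures and covariates, the primary outcome is the "agitation/aggression score (domain score on the Neuropsychiatric Inventory (NPI), continuous measure from 0-12, longitudinal". The responder outcome needs a 30% fall in a core score, the sum of motor activity and agitation/aggression, plus a CGI-C rating. The Power Analysis section makes effect sizes with 95% confidence intervals the main result. It states 80% power for an effect of 0.58-0.83 with 48 completers and does not mention patients who start without agitation.

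**The concern.** The list appears to contain a severity gate on three target behaviors, but the last alternative removes it. A patient with 4 points in one unrelated domain and nothing on the three target domains passes the NPI part of the rule.

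The gate as a whole also does not match the primary outcome, because none of its routes makes agitation necessary. The scale has a floor at 0, so a patient who starts there cannot contribute improvement on either arm and pulls the mean difference toward zero. Adjusting for baseline does not bring the lost effect back. A patient whose core score is 0 cannot show a 30% decrease, so the responder outcome is touched as well.

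At stake is the effect size meant to inform a larger trial, for which the Introduction foresees useful data on "low-dose lithium treatment for FTD patients with symptoms of agitation/aggression".

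**Working it through.** **1. The entry rule.** Inputs: the four alternatives in Prescreening item e. Assumption: total NPI is the sum of non-negative domain scores (the documents define only the core score as a sum).

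- If any domain is at least 4, the total is at least 4. Each domain route therefore lies inside the total-score route, and the rule reduces to total of at least 4. Enumerating domain scores confirmed this.
- With the clause, a patient with agitation 0, disinhibition 0, aberrant motor 0 and 4 points elsewhere passes the NPI part.
- Without the clause, that patient fails, but a patient with agitation 0 and aberrant motor 4 (or disinhibition 4) still passes.

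The clause therefore adds patients below 4 on all three target domains. It is not the only route in for patients with agitation 0.

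**2. The plan's own power figure.** Inputs from the Power Analysis section and the modeling section: 60 randomized, 20% attrition, 48 completers (24 per arm), two-sided 0.05. For a two-sample t-test, df = 46, the critical value is 2.013 and the noncentrality is d × √(24/2).

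- d = 0.826 gives noncentrality 2.86 and power 80.0%. At d = 0.83 power is 80.4%. The upper end of the stated range is reproduced.
- The 0.58 end needs a variance factor of (0.58/0.826)² = 0.49. The mean of six post-baseline visits with correlation 0.4 has factor (1 + 5 × 0.4)/6 = 0.50 and a detectable effect of 0.826 × √0.50 = 0.584. The plan does not state its correlation, so 0.58 is attainable but not confirmed.

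**3. Dilution.** Let f be the share of analyzed patients who start at 0 and cannot improve. The documents give no value, so f is an assumption. The raw mean difference falls to (1 − f) of its value. Two cases for the standardized effect:

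- SD unchanged: d × (1 − f).
- Mild case, floor patients stay at 0 and the SD shrinks by √(1 − f): d × (1 − f)/√(1 − f) = d × √(1 − f).

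With 24 per arm and d = 0.826 (80% power at f = 0):

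| f | d, SD unchanged | Power | d, mild case | Power |
|---|---|---|---|---|
| 10% | 0.743 | 71% | 0.784 | 76% |
| 20% | 0.661 | 61% | 0.739 | 71% |
| 30% | 0.578 | 50% | 0.691 | 65% |

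Starting from the 0.58 end gives the same powers. The effect there becomes 0.52-0.55, 0.46-0.52 and 0.41-0.49.

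**4. What a subset analysis gains.** Dropping only the floor patients leaves about 24 × 0.8 = 19 or 24 × 0.7 = 17 per arm. At d = 0.826 the powers are 70% and 65%. Against the all-patient figures this is a gain if the SD is unchanged (61% and 50%) but none in the mild case (71% and 65%).

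A cut at baseline 4 also drops scores 1-3, so it leaves fewer. With 15 per arm power is 59%, and with 12 per arm 49%. The half-width of the 95% interval in SD units is t × √(2/n): 2.013 × √(2/24) = 0.58 with 24 per arm, and 2.048 × √(2/15) = 0.75 with 15.

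**The case against.** The strongest reply is that breadth is partly intended. The Introduction names repetitive behaviors beside agitation and aggression, and mentions aberrant motor behaviors as a possible further target. The responder outcome uses a motor-plus-agitation core score, and motor activity has its own exploratory hypothesis. This stands. A reader might infer that the trial no longer studies the population it names, but the documents do not support that.

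The NPI rule is also not the only condition. A diagnosis with behavioral symptoms and a physician's note of disturbance are asked for too, and staff are told to look for agitation or repetitive behaviors in the chart. These conditions are real, but one list is open-ended and the other accepts any behavioral disturbance, so both can be met without agitation. The text is a prescreening list, and the screening packet's own criteria are not in the documents; they may be stricter.

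Three stronger readings also fail:

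- A reader might blame the total-score clause alone and expect its deletion to cure the mismatch. The disinhibition and aberrant-motor routes would remain.
- A reader might take the power loss as established, or as attributable to the clause. The floor share is assumed, and nothing splits it between routes of entry.
- A reader might say the power statement assumes that every patient can improve. It says no such thing. It gives a detectable standardized effect, in a pilot where estimation ranks above testing.

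**Conclusion.** The concern holds in limited form. Given a total that sums the domains, the three domain thresholds exclude nobody. Taking all routes together, no printed rule requires baseline agitation, while the primary outcome measures only that and has a floor at 0.

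The direction, dilution of the estimated effect, follows from the scale. The size does not follow from the documents: the power figures for floor shares of 10-30% are illustrations whose range depends on how far the variance shrinks. At a floor share of zero the plan's figures stand. The point merits a change because the effect size is the trial's stated main result and the remedy is cheap.

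**What to change.** **Main.** Pre-specify, before any unblinded analysis, that the primary week-12 contrast and its 95% confidence interval are also estimated in patients with baseline agitation/aggression of at least 4, using the same model and reported beside the all-patient estimate. Also report how many patients per arm started at 0. The subset is defined by a baseline score, so treatment cannot influence who is in it. The cost is one further model run on data already collected, with no effect on recruitment. The subset is smaller and its interval wider (see the 15-per-arm figures above). The gain is an undiluted estimate in patients with the target symptom, and it should not be presented as a gain in power.

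**Secondary.** Reconcile the total-score clause with the domain thresholds and with the screening packet. If the thresholds are meant to bind, remove the clause. If broad entry is meant, drop the thresholds and say so. Removing the clause costs some recruits and changes entry mid-trial, since this version of the manual dates from May 2021, after the study was adapted for COVID. By itself it does not exclude patients with agitation 0, so the subset estimate is needed either way.
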